They have another Axis I disorder as a principal diagnosis in the 6 months prior to screening;
They have a history of substance abuse or dependency in the 2 months prior to screening;
Pregnant women, lactating women, and women of childbearing potential not using medically accepted forms of contraception;
Patients with current or recent suicidality;
Scoring 10 or greater on the BDI
Scoring 2 or greater on the suicide question of the BDI
Psychotic disorders, bipolar disorder;
They are considered to be at a significant risk of committing homicide;
They have an unstable medical condition;
Women of childbearing potential (WOCBP) who are pregnant or are considering becoming pregnant during the length of the study;
They are regarded, for any reason by the principal investigator as being an unsuitable candidate for the protocol.
There has been a change in their medication or psychotherapy treatment regimen in the month preceding screening;

Mode of Administration: Patients will be randomly assigned to the active group or control group in a 1:1 ratio. Patients in the control group will be injected with a saline solution. Patients in the active group will receive 40 units of Botox (females) or 50 units (males). For females, 8 units will be injected into the procerus and 8 units into both the right and left medial and lateral corrugators. For males, 10 units will be injected into each location.

Method of Blinding: This will be a double-blind study. The clinician administering the injections will be blinded. After the initial visit, to help maintain the blind, all data will be collected via a web portal with online questionnaire assessments.

Duration of Treatment: The study will be divided into three phases: screening and enrollment, treatment, and follow-up. Patients who meet all criteria will be randomized at the screening visit. The follow-up phase will last eight (8) weeks after the investigational product is administered. Patients will be instructed to complete the LSAS and BDI online at week 4 and 8.

General Design and Methodology: Prior to screening, potential participants will fill out the LSAS and BDI online in order to determine initial eligibility. Those who meet the criteria will be

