scheduled for an in-person screening visit. At screening, patients will sign consent and be diagnosed by means of the MINI (Sheehan et al,1998) , and will have a DSM-IV diagnosis of Social anxiety disorder (SAD). They will complete the LSAS. They will also complete the patient-rated BDI (Beck et al.,1961). Patients who meet all criteria will be randomly assigned to receive either the investigational product or placebo. Patients will be photographed, at the initial visit, at rest. The study medication or placebo will be injected within 7 days of clinical assessments into the procerus and corrugator supercilii frown muscles of each patient by a physician's assistant who is experienced in the administration of this medication. Four weeks \pm 7 days, and eight weeks \pm 7 days following the injection, each patient will complete online assessments. Patients will complete online the adverse events (AEs) and concomitant medications questionnaires will be at week 4 and 8.

Investigational New Drug (IND) Application: This study is exempt from the requirement for an IND submission based on the following criteria: Botox is lawfully marketed in the United States. There is no intent to report the findings of this trial to the FDA in support of a new indication or any significant change in the labeling of the drug. This study is not intended to support a significant change in the advertising of the prescribed drug. Compared to the current labeling of Botox, there will be no change in the route of administration, the dosage level, or any other factor that significantly increases the risk, or decreases the acceptability of the risk, associated with the use of the drug. Botox is approved for doses up to 400 units. We will use 40 or 50 units. The patient population will be different compared to the current labeling, which specifies bladder dysfunction, chronic migraine, upper limb spasticity, cervical dystonia, blepharospasm, strabismus and primary axillary hyperhidrosis. The change in population will not significantly increase the risk. All participants in the study will be medically stable adults.

BACKGROUND INFORMATION

Introduction

Investigational Treatment

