All procedures except photography and administration of investigational product will take place in the clinical offices of GWU MFA. For photography and administration of the investigational product, patients will be transported by taxi or private car service to the Chevy Chase Cosmetic Center, located at [name]. After the study procedures are complete, participants will be transported back to GWU MFA or to a nearby Metro station, if they prefer.

The injectable syringes will be prepared by [name] at the Chevy Chase Cosmetic Center. Syringes will contain either Botox or saline based on the randomization scheme. They will be marked with numbers written on tape affixed to clear envelopes that contain only the individual syringes. After being made, syringes will be stored in a refrigerator at 4 degrees Celsius in the Chevy Chase office. All patients will be examined and injected by a physician assistant, [name], who has been trained in the practice of injection, and was the injector for the Finzi and Rosenthal clinical trial studying Botox for the treatment of major depressive disorder. [name] will have no contact with patients, to maintain the blind.

The study medication or placebo will be injected into the procerus and corrugator supercilii frown muscles of each patient by a physician or physician's assistant.

Four and eight weeks following the injection, patients will be contacted and asked to complete the online LSAS and BDI self-assessments as well as reporting on concomitant medications and adverse events.

Participants will receive a gift card for up to \$45 at the completion of the study. They will receive \$25 if they complete the screening visit, and additional \$10 if they complete the first post-treatment online assessment, and another \$10 if they complete the second post-treatment online assessment.

Safety Measures

Adverse events will be collected via online assessments, and will be reviewed by the investigator within 24 hours. Patients will be contacted by telephone, or asked to come in for a face-to-face meeting if the investigator believes that the patient is at risk or if further evaluation of the adverse event is needed. Patients will be instructed to contact the investigator by telephone at any time if they have concerns about adverse events they may be experiencing.

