All adverse events that occur during the study period, that is, from the signing of the informed consent through the follow-up period, will be documented regardless of the severity of the event or judged relationship to the study treatment. The clinical course of each adverse event will be monitored until resolved or stabilized, until the patient is referred to the care of a local health care professional, or until determination of a cause unrelated to the study technique or study procedure is made.

The investigator will capture onset and resolution dates, duration, action taken, treatment administered and outcome for each adverse event. The relationship of the adverse event to study treatment and procedures and the severity and seriousness will also be recorded.

Serious Adverse Events

Adverse events are classified as either serious or non-serious. A serious adverse event is any adverse event that results in any of the following outcomes or actions:

Death

A life-threatening adverse event (i.e., the patient was at immediate risk of death from the event as it occurred); does not include an event that, had it occurred in a more severe form, might have caused death

Inpatient hospitalization or prolongation of existing hospitalization

A persistent or significant disability/incapacity

A congenital anomaly/birth defect

An important medical event that may not result in death, be life-threatening, or require hospitalization, but may jeopardize the patient and may require medical or surgical intervention to prevent one of the outcomes listed in this definition

Hospitalizations scheduled for an elective procedure or for treatment of a preexisting condition that has not worsened during participation in the study will not be considered serious adverse events.

Other Safety Measures and Variables: Concomitant Therapy or Medication

Co-administration of Botox and aminoglycosides or other agents interfering with neuromuscular transmission (e.g., curare-like nondepolarizing blockers, lincosamides, polymyxins, quinidine, magnesium sulfate, anticholinesterases, succinylcholine chloride) should only be performed with caution as the effect of the toxin may be potentiated.

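### After injection, adverse events are first asked about at day 21 to 35; earlier mild events depend on a patient's call or on recall

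*Combined protocol and SAP*

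**What the plan says.** The General Design and Methodology part of the protocol summary sets the schedule: "Patients will complete online the adverse events (AEs) and concomitant medications questionnaires will be at week 4 and 8". It gives both time points a window of 7 days either side, counted from injection. The Study Design section repeats the schedule: at four and eight weeks patients are contacted for the LSAS and BDI "as well as reporting on concomitant medications and adverse events". Under Method of Blinding, the web portal is the route for everything after the first visit: "After the initial visit, to help maintain the blind, all data will be collected via a web portal with online questionnaire assessments".

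Three other provisions bear on the early period:

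- **Injection visit (Study Design).** "All patients will be examined and injected by a physician assistant".
- **Patient-initiated route (Safety Measures).** "Patients will be instructed to contact the investigator by telephone at any time if they have concerns about adverse events they may be experiencing".
- **Review and contact step (Safety Measures).** "Adverse events will be collected via online assessments, and will be reviewed by the investigator within 24 hours". Staff then telephone or see the patient "if the investigator believes that the patient is at risk or if further evaluation of the adverse event is needed".

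Safety Measures also states the aim. All events from consent to the end of follow-up "will be documented regardless of the severity of the event or judged relationship to the study treatment". For each event the investigator records when it began and ended, among other details, and follows its course until it resolves or stabilizes, the patient is referred to local care, or an unrelated cause is established.

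**The concern.** The commitment covers events of any severity, with dates and follow-up. The schedule asks nothing between the injection visit and the week 4 form. The telephone instruction has a narrower trigger than the commitment: it applies to a patient who is concerned, whereas the commitment also covers an event too slight to cause concern. A mild or brief event that starts and resolves before the first form, with no call, is not followed while it lasts. Whether it is recorded, and with what dates, then depends on memory.

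At stake are early participant follow-up and the completeness and dating of the adverse-event record. The efficacy analysis does not use these data.

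**Working it through.** The documents give no figure for this point, so there is none to reproduce. The check is day arithmetic on the stated windows.

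**Inputs from the protocol.** Forms fall at 28 ± 7 and 56 ± 7 days after injection (General Design and Methodology). About 30 patients are randomized (Study Design).

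**Input assumed by the reviewer.** One added form is completed on day d, with 7 ≤ d ≤ 14.

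**Current schedule.**
- First form: 28 − 7 = day 21 to 28 + 7 = day 35.
- Second form: 56 − 7 = day 49 to 56 + 7 = day 63.
- Span from injection to first question: 21, 28 or 35 days if the week 4 form is early, nominal or late.
- Span between the two forms: 49 − 35 = 14 days to 63 − 21 = 42 days.

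**With the added form.** If the week 4 form is completed on day W, the longest span without a question up to week 4 is max(d, W − d).

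| W | Now | Longest span with added form | Reduction |
|---|---|---|---|
| 21 | 21 | at most 14 (d = 7 or d = 14) | at least 21 − 14 = 7 |
| 28 | 28 | 14 (d = 14) to 21 (d = 7) | 28 − 21 = 7 to 28 − 14 = 14 |
| 35 | 35 | 21 (d = 14) to 28 (d = 7) | 35 − 28 = 7 to 35 − 21 = 14 |

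Across the windows the reduction is 7 to 14 days. The week 4 to week 8 span stays at 14 to 42 days.

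**Workload.** 30 × 2 = 60 scheduled forms become 30 × 3 = 90.

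**Do the other provisions fill the early period?**
- The physician assistant can observe an immediate reaction, and that could prompt investigator contact. No enquiry after the injection visit is described.
- The 24-hour review of online reports needs a submitted report, and none is scheduled before day 21.
- The staff contact step rests on the investigator's belief that there is a risk or something to evaluate, so some information must arrive first.
- The telephone route needs the patient to raise the event.

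None of the four asks about an event that the patient does not volunteer.

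**Onset timing.** The only timing in the documents is in Known and Potential Risks and Benefits to Human Subjects, which puts symptoms of spread beyond the injection site at hours to weeks after injection, in some cases at higher doses. This shows that the early weeks are a relevant period. It does not show that events cluster before day 21.

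**The case against.** The strongest reply is that no stated rule is broken. Safety Measures promises documentation but fixes no contact frequency, and calls plus recall can formally meet the promise. That stands: a reader might infer a contradiction between the schedule and the commitment, and the text does not support one.

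A reader might also infer that before the first form only the patient's own call can start the contact step. That is too strong. The step turns on what the investigator believes, and a reaction seen by the physician assistant could trigger it.

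Nor do the documents support a reading that serious distant spread would go unnoticed. The risk section reports no definitive serious cases of it with dermatologic use for glabellar lines, and a worrying event would probably prompt a call.

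Other parts of the reply also stand. The week 4 form can still recover an early event, and the investigator can telephone to clarify dates. Both arms share the schedule, so under-capture need not by itself bias the comparison between them. The adverse-event form is not among the attachments listed in the Appendix and the consent pages are not available here. How the form asks about past events, and what patients are told about early symptoms, therefore cannot be judged.

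Finally, the remedy is partial. It is still retrospective over 7 to 14 days, leaves the span of up to 42 days between the scheduled forms untouched, and adds a symptom prompt before the self-rated week 4 LSAS, a primary outcome. These points limit the benefit. They do not remove the gap, because none of the existing safeguards asks about a mild event that the patient does not raise.

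**Conclusion.** The concern holds as a minor weakness in ascertainment. The first solicited adverse-event report comes 21 to 35 days after injection. Earlier capture depends on observation at the injection visit, a patient's call or later recall, so the dates of a mild early event may rest on up to 35 days of memory.

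The number of events lost or misdated cannot be derived from the documents. The stated gain of 7 to 14 days describes the schedule only, and it rests on the assumed day 7 to 14 timing and on forms being completed within their windows. Confidence is medium, because the content of the form is unknown. A reader might take the gap as a threat to the efficacy result, but nothing in the documents supports that.

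**What to change.** In General Design and Methodology and in Study Design, add a sentence such as: Patients will also complete the online adverse events questionnaire once between day 7 and day 14 after injection. Send the existing form automatically to both arms, without the LSAS or BDI, and apply the same 24-hour review and contact step. Keep the week 4 and week 8 forms and the telephone instruction as they are. No visit is added, and the form stays within the web portal that the blinding section relies on.

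The cost is up to 30 more forms to review and a slight patient burden. There is also a marginal added chance of allocation guessing: the prompt is the same in both arms but the answers may differ. The same form is already due around each LSAS, so this increment is small.

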A Controlled Study of the Efficacy of Botulinum Toxin A (Botox) for the Treatment of Social Anxiety Disorder (SAD)

[name]
[name], PhD

CONTACT INFORMATION

Primary contact:
[name], [contact], [contact]

CLINICAL STUDY PROTOCOL SUMMARY

Sponsor: Dermatology and Cosmetic Surgery Associates, LLC

Investigational Treatment: Five injections of Botox will be administered at a single treatment visit.

Title of Study: A Controlled Study of the Efficacy Botox Treatment for the Treatment of Social Anxiety Disorder (SAD)

Date: 3/8/2016

Number of centers: One

Primary Objective: The objective of this proposed study is to obtain data on the efficacy of Botox in reducing symptoms of social anxiety disorder (SAD) in male and female patients between the ages of 18 and 65 years old. Efficacy will be determined by using a continuous measure of outcome, the Liebowitz Social Anxiety Scale (Primary outcome) (LSAS; Fresco et al, 2001) and dichotomous indicators of response (Primary outcome) (LSAS <50) and remission (Secondary Outcome) (LSAS <30). Subjects will be assessed using: the self-rated LSAS and the self-rated version of the BDI-I at screening, 4 weeks, and 8 weeks.

Statistical Considerations: An ANOVA with repeated measures to determine whether there are statistical differences between the interventions will be used. Because the effect size of the intervention is unknown, the power statistics required to obtain significant differences between placebo and Botox cannot be calculated.

Number of Patients Planned: Up to 100 subjects will be screened in order to enroll 30.

Diagnosis and Criteria for Inclusion: Patients will be included in this study if they meet all of the following criteria:

Written informed consent is obtained;
They are a 18 to 65 years old;

A primary diagnosis for SAD as diagnosed by the MINI, and their current episode must be at least one month in length; A total score on the LSAS of 60 or greater
Women of childbearing potential (WOCBP) are on an acceptable form of birth control and are not pregnant or lactating;
They are judged by the investigator to have the capacity to understand the nature of the study;
They are willing to comply with all the requirements of the study.
They are considered by the investigator to be likely to adhere to the protocol.

Criteria for Exclusion: Patients will be excluded from this study if they meet any of the following criteria:

They have ever been treated with botulinum toxin A ;

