The effect of administering different botulinum neurotoxin serotypes at the same time or within several months of each other is unknown. Excessive neuromuscular weakness may be exacerbated by administration of another botulinum toxin prior to the resolution of the effects of a previously administered botulinum toxin.

Stopping Rules and Discontinuation Criteria

A participant may discontinue participation in the study at any time for any reason (e.g., lack of efficacy, consent withdrawn, or adverse event). The investigator may discontinue a patient from the study at any time for any reason (e.g. non-adherence to the protocol, emergence of psychiatric instability).

Confidentiality and Privacy Regarding Participants

The investigator will assure the privacy of all patients, including their personal identity and all personal medical information at all times. Data will be stored on the secure REDCap system or on a password-protected computer in a locked office. Hard copies of data will be stored in a locked office, and destroyed after the data is entered into a computer. Participants will be assigned a code number, and all data will be identified by this code. The code key will be kept separate from the data, and will be destroyed five years after publication of the study results. Photographs of the participants will be altered to eliminate the possibility of identification five years after publication of the study results. This will entail cropping out the entire face except for the area that was injected. The retained image will not include the participants' eyes, or any features below the eyes. The remaining, fully anonymized data will be kept indefinitely. Privacy will be assured by conducting all in-person procedures in private clinical offices or exam rooms.

Conflict of Interest

[name], PhD, a sub-investigator on the study, holds a patent on the use of Botox for social anxiety disorder. The conflict of interest will be managed in the following way: [name] will prepare the investigational product according to the randomization scheme. He will have no contact with participants. He will not collect or analyze data. The principal investigator, who has no conflict of interest, will approve all manuscripts prior to submission and publication.

REFERENCES

Carruthers A. Botulinum toxin type A: history and current cosmetic use in the upper face. *Dis Mon* 2002; 48: 299.

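### With all treatment given at one visit, leaving the study can mainly end LSAS and BDI collection, and the plan covers neither follow-up of those who leave nor analysis of incomplete scores

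*Combined protocol and SAP*

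**What the plan says.** The protocol summary, under Investigational Treatment, says: "Five injections of Botox will be administered at a single treatment visit". The injection follows the clinical assessments within 7 days. After it, the patient's scheduled tasks are online forms at weeks 4 and 8.

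Under Stopping Rules and Discontinuation Criteria there are two rules, both applying to the study and not to treatment. For the patient: "A participant may discontinue participation in the study at any time for any reason (e.g., lack of efficacy, consent withdrawn, or adverse event"). A separate rule covers the investigator, who "may discontinue a patient from the study at any time for any reason (e.g. non-adherence to the protocol, emergence of psychiatric instability").

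On follow-up, Study Design says that at four and eight weeks "patients will be contacted and asked to complete the online LSAS and BDI self-assessments as well as reporting on concomitant medications and adverse events". It pays $10 for each post-treatment assessment completed. It does not say whether patients who have discontinued are included.

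On analysis, Statistical Considerations says: "An ANOVA with repeated measures to determine whether there are statistical differences between the interventions will be used". No section gives an analysis set, a rule for missing scores or an expected number of discontinuations.

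**The concern.** In a trial with continuing treatment, a patient can stop treatment and still be followed. Here treatment is complete after one visit, so a rule about leaving the study bears mainly on outcome data. Some of the reasons given as examples, such as lack of efficacy and psychiatric instability, are plausibly related to the LSAS score, which is the primary outcome. The scores missing would then tend to be the poor ones.

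Two gaps combine. The discontinuation section does not keep such patients in data collection, and the analysis section does not say what happens to a patient with only one follow-up score. With about 15 patients per arm, each one missing leaves that arm's response proportion (LSAS below 50) uncertain by 1/15 = 6.7 percentage points.

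**Working it through.** **Inputs from the protocol.** About 30 patients are randomised 1:1, so 30/2 = 15 per arm. Treatment is one visit, with follow-up LSAS at weeks 4 and 8. The protocol says the effect size is unknown and power cannot be calculated, so it has no figure to reproduce.

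**Assumptions, not in the protocol.** The true effect is 0.8 SD (or zero). LSAS is normal with SD 1, higher being worse. A patient leaves when a latent reason, correlated ρ with the score, passes a threshold common to both arms. Either 6.7% (about one patient) or 20% of controls leave. The test is a two-sided 5% t-test on those remaining, standing in for the ANOVA.

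**Step 1: what is lost, by time of leaving.**

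| Patient leaves | Lost |
|---|---|
| Between randomisation and injection | Possibly treatment, and both follow-up scores |
| After injection, before week 4 | Both follow-up scores |
| After the week 4 forms | Week 8; also week 4 if the ANOVA uses complete cases |
| After the week 8 forms | Nothing |

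After the initial visit, "all data will be collected via a web portal with online questionnaire assessments". Leaving before week 4 would therefore need an unscheduled contact, which Safety Measures allows: "Patients will be instructed to contact the investigator by telephone at any time".

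**Step 2: expected shift, one follow-up score.** If a share f of controls leaves, the threshold is c = z(1 − f). The mean of the remaining controls moves by −ρφ(c)/Φ(c). For the active arm, c is replaced by c + 0.8ρ.

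- f = 6.7%, ρ = 0.5: c = 1.501. Controls move by −0.5 × 0.1293/0.9333 = −0.069. In the active arm c = 1.901, 2.9% leave, and the move is −0.5 × 0.0655/0.9714 = −0.034. Observed difference: 0.800 − 0.069 + 0.034 = 0.765, in line with the simulated 0.764.
- f = 20%, ρ = 0.5: c = 0.842. Controls move by −0.5 × 0.2800/0.8 = −0.175. In the active arm c = 1.242, 10.7% leave, and the move is −0.5 × 0.1846/0.8928 = −0.103. Observed difference: 0.800 − 0.175 + 0.103 = 0.728 (simulated 0.730).
- No true effect: both arms move equally, so the bias is zero. Simulated rejection is 4.9–5.0%.

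**Step 3: power by simulation (200,000 trials per setting, true effect 0.8 SD).**

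| Setting | Difference (SD) | Power |
|---|---|---|
| No loss | 0.80 | 56.2% |
| ρ = 0.5, 6.7% of controls | 0.76 | 52.2% |
| ρ = 0.5, 20% of controls | 0.73 | 45.1% |
| ρ = 0.3, 6.7% of controls | 0.79 | 53.0% |
| ρ = 0.3, 20% of controls | 0.77 | 46.3% |
| Random loss at the ρ = 0.5, 6.7% rates | 0.80 | 54.0% |
| Random loss at the ρ = 0.5, 20% rates | 0.80 | 48.4% |

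Ordinary attrition therefore explains 56.2 − 54.0 = 2.2 of the 4.0 points lost at 6.7% (55%), and 56.2 − 48.4 = 7.8 of the 11.1 points lost at 20% (70%).

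**Step 4: leaving only after week 4.** This uses the mean of both visits, visit correlation 0.6, ρ = 0.5 with the week 4 score, and equal true effects at both weeks.

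| Analysis | 6.7% of controls leave | 20% of controls leave |
|---|---|---|
| Full data | 0.80 SD, 66% | 0.80 SD, 66% |
| Completers only | 0.77 SD, 62% | 0.74 SD, 54% |
| Week 4 score kept when week 8 is missing | 0.81 SD, 65% | 0.81 SD, 64% |

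The last row is a simple available-score mean, a stand-in for a likelihood-based model. It slightly overshoots 0.80 because a leaver's high week 4 score stands alone instead of being averaged with week 8. With visit correlation 0.8, completers only gives 0.769 SD and 56.7%, or 0.735 SD and 49.1%, against 0.80 SD and 60.7% with full data.

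**The case against.** The discontinuation section is an ordinary statement of the right to leave. A reader might infer that it orders outcome collection to stop. It does not, and the follow-up sentence, which makes no exception, can be read to cover everyone injected. That stands: the gap is silence, not contradiction.

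The routes out are few. After injection a patient has only two sets of online forms to complete, each paid, so there is little to leave. The exclusions (for example a BDI of 10 or more, suicidality, or a recent treatment change) should make removals for instability rare. Much of the real loss may be plain non-response, which wording on discontinuation would not cure. This stands as a limit on size, but neither the contact sentence nor the payment settles what happens to those who have left.

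The strongest objection is that the analysis rule matters more than the discontinuation wording. For patients leaving after week 4, using the available scores restores nearly all the loss with no further follow-up. That is accepted, and the fix starts there. Continued collection adds most for patients who leave before week 4.

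The protocol does not say how the ANOVA would treat incomplete cases. Dropping them is the standard form of the method, not a stated choice.

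**Conclusion.** The point holds as a minor to moderate improvement that costs little. The protocol lets patients leave, or be removed, for reasons related to outcome when little but outcome collection remains to end. It neither keeps them in collection nor protects the scores already given.

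The likely effect is modest. With an assumed 0.80 SD effect and about one control lost, the difference falls to 0.76–0.79 SD and power by 3 to 4 points. With 20% of controls lost it falls to 0.73–0.77 SD and power by 10 to 11 points. Effect size, share leaving, correlations and the common threshold are all assumed, so these figures illustrate and do not predict.

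Three stronger readings are not supported.

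- **Bias in favour of Botox, or extra false positives.** Under the double blind the same threshold can be expected in both arms. The bias is then zero if Botox has no effect, and the difference shrinks if it works.
- **A large one-sided shift.** Losing the worst 1 to 4 of 15 patients from one arm only would move that arm's mean by about 0.14 to 0.45 SD. Nothing in the protocol suggests such one-sided loss.
- **Loss of safety data.** Adverse events "from the signing of the informed consent through the follow-up period, will be documented", so they are outside this point.

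**What to change.** 1. **Statistical Considerations.** Analyse all randomised patients in the arm assigned, with a likelihood-based repeated-measures model that uses the week 4 score when week 8 is missing. Add a sensitivity analysis for missing LSAS.
2. **Stopping Rules and Discontinuation Criteria.** State that after injection the week 4 and week 8 online forms are still sought from every randomised patient, unless that patient withdraws consent to data collection. Record the reason for and date of each discontinuation.

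The cost is a few sentences and some reminders, since the forms are already online. Some discontinued patients will not reply, so recovery will be partial. Some later scores may reflect other treatment started after leaving; the existing concomitant medication form would show this for medication. The change concerns data collection and analysis only and takes no view on when a patient should be discontinued.
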